1 PROTOCOL SUMMARY

1.1 Synopsis

- Title:** Phase 2 study of the PTH-independent Effects of Encaleret on Mineral Homeostasis in subjects with post-surgical hypoparathyroidism (PSH)
- Study Description:** This will be a single-site, proof-of-principle, open-label study to explore the PTH-independent effects of encaleret on calcium homeostasis in participants with low or undetectable PTH levels as a result of neck surgery (PSH).
- Objectives:** *Primary Objective:*
- Evaluate the PTH-independent effects of encaleret on renal calcium handling in participants with PSH.
- Secondary Objectives:*
- Evaluate the ability of encaleret to normalize blood calcium while maintaining a normal urinary calcium in participants with PSH.
- Tertiary/Exploratory Objectives:*
- Evaluate the ability of encaleret to increase serum iPTH levels in participants with PSH.
 - Evaluate the effect of encaleret on 1-alpha hydroxylase action by measuring 1,25-(OH)₂ Vitamin D levels.
 - Explore the dynamic effect of encaleret on blood and urinary calcium, iPTH, cAMP, 1,25-(OH)₂ Vitamin D, and urinary citrate.
 - Evaluate the effect of encaleret on bone turnover in participants with PSH.
 - Evaluate the effect of encaleret on phosphate, magnesium, and FGF23 levels.
 - Explore the effects of encaleret on 24-hour urine markers that impact stone formation
 - Examine the PK of encaleret in participants with PSH and explore PK-PD interactions.
 - Explore the effect of encaleret on bone and mineral homeostasis in the following sub-groups, *as defined in Section 9.3:*
 - Permanent hypoparathyroidism (Cohort 1)
 - Recent hypoparathyroidism (Cohort 2)
 - “PTH-Clamp” cohort
 - “Aparathyroid” cohort
 - Hyperthyroid cohort
 - Normothyroid cohort
 - Thyroid cancer cohort

2

Primary Endpoint:

- Percent change in Fractional Excretion of Calcium (FECa) from baseline (Day -1) to the final day of treatment (Day 6 or the last measurement while on encaleret). FECa calculated using fasting blood levels and spot urine collection.

Secondary Endpoints:

- Proportion of participants who achieve a concomitant normal or elevated fasting blood calcium (albumin-corrected calcium >8.5 mg/dL) and a normal 24-hour urinary calcium level (<250 mg/24 hours for women, <300 mg/24 hours for men) on encaleret at any point between day 1 and day 5.

Tertiary/Exploratory Endpoints:

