3 OBJECTIVES AND ENDPOINTS

OBJECTIVES	ENDPOINTS	JUSTIFICATION FOR ENDPOINTS
Primary		
Evaluate the PTH-independent effects of encaleret on renal calcium	Percent change in Fractional Excretion of Calcium (FECa) from baseline (Day -1) to the final day	FECa reflects the relationship between blood calcium and

OBJECTIVES	ENDPOINTS	JUSTIFICATION FOR ENDPOINTS
handling in participants with PSH.	of treatment (Day 6 or the last measurement while on encaleret). FECa calculated using fasting blood levels and spot urine collections.	urinary calcium. CaSR modulation by encaleret is expected to directly affect FECa. If a patient stops encaleret early prior to Day 6, the last fasting FECa on encaleret 162 mg BID will be used for this endpoint.
Secondary		
Evaluate the ability of encaleret to normalize blood calcium while maintaining a normal urinary calcium in participants with PSH.	Proportion of participants who achieve a concomitant normal or elevated fasting blood calcium (albumin-corrected calcium >8.5 mg/dL) and a normal 24-hour urinary calcium level (<250 mg/24 hours for women, <300 mg/24 hours for men) on encaleret at any point between day 1 and day 5.	Clinically relevant endpoint to determine if encaleret can allow PSH to have both normal blood and urinary calcium.
Tertiary/Exploratory		
Evaluate the ability of encaleret to increase serum iPTH levels in participants with PSH.	Change in blood iPTH comparing average baseline iPTH to average peak iPTH on encaleret. The average baseline iPTH will include all baseline iPTH levels from the screening visit, Day -1, and pre-dose on Day 1. The average peak iPTH will average the peak iPTH levels on every day the patient is on encaleret (days 1 to 5). An increase in iPTH will be	Averaging iPTH will prevent spurious excursions from impacting outcomes

OBJECTIVES	ENDPOINTS	JUSTIFICATION FOR ENDPOINTS
	considered clinically significant if there is an increase both by 50% AND by more than 10 pg/dL.	
Evaluate the effect of encaleret on 1-alpha hydroxylase action by measuring 1,25-(OH) ₂ Vitamin D levels.	Change in 1,25-(OH) ₂ Vitamin D on encaleret comparing the maximal level prior to receiving calcitriol (On Days 3-5) to baseline (Average of Day 1 Pre-dose levels). Increase will be considered significant if there is an increase of more than 50%. Participants who receive calcitriol prior to Day 3 will be excluded.	

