Participants who develop abnormal clinical or laboratory assessments that indicate continuation of the treatment may put the subject at risk, may have their encaleret dosing interrupted at the discretion of the principal investigator.

Participants who met specific achievement thresholds for both the primary and secondary endpoints may be eligible for early drug discontinuation at the discretion of the principal investigator. The defined thresholds are as follows: The primary endpoint will be considered achieved if the fasting FECa has decreased by >40%. The secondary endpoint will be considered achieved if the participant has achieved concomitant normal or high blood calcium and normal urinary calcium. This approach aims to facilitate the evaluation of the PK-PD relationship (exploratory endpoint) during encaleret withdrawal.

Calcium and calcitriol supplementation and encaleret dose will be adjusted following the algorithm delineated in Table D with the primary goal of safety.

Drug Administration

Encaleret will be dispensed by the NIH Pharmacy. It will be provided as film-coated tablets containing the active ingredient encaleret provided in 54 mg dosage strength. Participants will receive encaleret 162 mg (3 tablets) every 12 hours per protocol with water.

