9 STATISTICAL CONSIDERATIONS

9.1 Statistical Hypothesis

Encaleret in PSH will decrease the fractional excretion of calcium comparing baseline (Day - 1) to the last 24-hour period a patient was taking encaleret 162 mg BID. FECa will be calculated using 24-hour urine and 4-hour post-prandial blood levels.

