9.2 Sample Size Determination

The proposed clinical trial is primarily exploratory and preliminary data is limited. The primary study endpoint is the percent decrease in FECa using the entire Treatment Population (all participants who received at least one dose of study drug). Participants withdrawing for any reason any time after receiving their first dose of the study drug will remain in the Treatment Population, and the final FECa used will be the last fasting timepoint during which the patient was taking encaleret 162 mg BID.

Power calculations were based on the prior experience with encaleret in ADH1. In the ADH1 cohort, during a 5-day dosage escalation study (period 1), when 6 subjects were on the maximal dose of 162 mg BID for 3 days, the Mean (Standard deviation) of the Day 6 change in fasting FECa from baseline was -66 (20) % (unpublished data). Using a two-tailed 0.05 level paired t-test, we found that 15 participants yielded 80% power to detect a percent change of 16%; 10 participants yielded 80% power to detect a percent change of 20% and 5 participants yielded 80% to detect a percent change of 34%. Given the mean reduction in FECa was 66% in the ADH1 cohort (and the kidneys of participants with PSH might be expected to respond even more robustly to encaleret), we anticipate even a sample size of 5 would be sufficient to confirm the proof-of-principle effect on FECa.

Nevertheless, we plan to enroll up to 15 participants in this study in order to increase the likelihood that we include participants with a range of residual parathyroid tissue and to include participants with recent hypoparathyroidism. This will allow for sub-group analysis (see Section 9.3), which will be exploratory and hypothesis generating.

Of note, we plan to enroll only 5 participants with recent PSH (Cohort 2), because we anticipate some challenges in enrolling this population. More than 5 participants may be impractical to enroll in a reasonable amount of time.

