9.4.2 Analysis of the Primary Endpoints

The primary endpoint is the percent change in FECa from baseline to the last day on encaleret 162 mg BID. If a subject stops encaleret early or decreases the dose, the FECa will be calculated using the last fasting labs when the patient was on encaleret 162 mg BID. For this primary endpoint, if the normality assumption holds, one-sample t-test will be used to analyze the data. Otherwise, the nonparametric alternative, the Wilcoxon signed-rank test will be used.

The primary endpoint analysis will be conducted in the Treatment Population.

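### Section 9.1 states the primary hypothesis for a different FECa from the one that defines the primary endpoint, and the sampling tables fully support neither

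*Combined protocol and SAP*

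**What the plan says.** The Synopsis (Section 1.1) gives the primary endpoint as "Percent change in Fractional Excretion of Calcium (FECa) from baseline (Day -1) to the final day of treatment", meaning Day 6 or the last measurement on encaleret, and specifies "FECa calculated using fasting blood levels and spot urine collection". The table in Section 3 repeats this: "FECa calculated using fasting blood levels and spot urine collections".

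Section 9.1 states the hypothesis as a fall in FECa from Day -1 "to the last 24-hour period a patient was taking encaleret 162 mg BID", and adds: "FECa will be calculated using 24-hour urine and 4-hour post-prandial blood levels".

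Three other places refer to fasting FECa:

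- Section 9.2, in a sentence about participants who withdraw after their first dose: "the final FECa used will be the last fasting timepoint during which the patient was taking encaleret 162 mg BID".
- Section 9.4.2, for a participant who stops early or reduces the dose: "the FECa will be calculated using the last fasting labs when the patient was on encaleret 162 mg BID".
- Section 6.1.2, under early drug discontinuation: "The primary endpoint will be considered achieved if the fasting FECa has decreased by >40" per cent.

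No section reconciles the two versions or labels the one in Section 9.1 as secondary, exploratory or a sensitivity measure.

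**The concern.** The hypothesis and the endpoint should describe one variable. Here a programmer reading Section 9.1 and one reading Section 1.1 would calculate different numbers for the same participant.

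The trial is open-label and single-arm with one primary test, so an unsettled primary variable leaves room for choices once data are visible. Other decisions refer to the same variable: Section 6.1.2 uses a fasting FECa threshold, and Section 10.2 lists a finding that the primary endpoint has been met among the reasons that may warrant ending the study. Section 9 could also be read as applying the Section 9.1 formula to completers and fasting values to early stoppers, which would put two quantities into one t-test.

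**Working it through.** **1. The two definitions side by side**

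| Element | Sections 1.1 and 3 | Section 9.1 |
|---|---|---|
| Urine | spot | 24-hour |
| Blood | fasting | 4 hours post-prandial |
| On-treatment time | Day 6, or last measurement on drug | last 24-hour period on 162 mg BID |

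All three elements differ.

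**2. Does Section 9 settle the matter elsewhere?** Not for completers. The fasting wording in 9.2 is attached to withdrawals, and in 9.4.2 to early stop or dose decrease. The general rule in 9.4.2 refers only to the last day on 162 mg BID. Neither section names a urine sample. Within Section 9, only 9.1 names both specimens.

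**3. Can each version be formed from the schedule?** The documents print no FECa formula. I assume the usual one, (urine Ca × blood Cr) / (blood Ca × urine Cr), which needs calcium and creatinine in both specimens.

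| Sample needed | Day -1 | End of treatment |
|---|---|---|
| Endpoint: fasting blood | listed (Table C) | listed: Day 5 24-hour draw, the Day 6 morning (Table C) |
| Endpoint: spot urine Ca, Cr | listed (Table B) | not listed; nearest is the Day 5 16-24 hour timed collection |
| 9.1: 24-hour urine | listed (Table B) | listed (Table B) |
| 9.1: post-prandial blood | not listed; only fasting labs (Table C) and an evening panel of Ca, Mg, PO4 and albumin without creatinine (Table A) | a 4-hour draw on Days 1 to 5, timed from the morning dose |

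The Section 9.1 version lacks its baseline blood. The endpoint version lacks its on-treatment urine, because Table B lists spot urine Ca and Cr only on Day -1 and at Day 1 Time 0.

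**4. Which version does the sample size support?** Inputs from Section 9.2: mean -66%, SD 20%, from fasting FECa in 6 subjects with ADH1; paired t-test, two-sided 0.05, 80% power. Power is the probability that a noncentral t variable with n - 1 degrees of freedom and noncentrality (change / SD) × √n exceeds the two-sided critical value in absolute size.

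| n | Stated change | Noncentrality | Power at stated change | Change detectable at exactly 80% |
|---|---|---|---|---|
| 15 | 16% | 16/20 × √15 = 3.098 | 0.821 | 15.56% |
| 10 | 20% | 20/20 × √10 = 3.162 | 0.803 | 19.92% |
| 5 | 34% | 34/20 × √5 = 3.801 | 0.808 | 33.64% |

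The stated figures are the exact ones rounded up, so the plan's arithmetic is right, for fasting FECa. The documents give no SD for the Section 9.1 version. Under assumed SDs:

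| Assumed SD | Detectable change, n = 15 / 10 / 5 | Power for 66%, n = 15 / 5 |
|---|---|---|
| 20% | 15.6 / 19.9 / 33.6% | 1.000 / 0.999 |
| 30% | 23.3 / 29.9 / 50.5% | 1.000 / 0.949 |
| 40% | 31.1 / 39.8 / 67.3% | 1.000 / 0.786 |
| 60% | 46.7 / 59.8 / 100.9% | 0.977 / 0.466 |

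The plan's remark that even 5 participants would be enough therefore carries over to the Section 9.1 version only if its SD is not much above 30%. With 15 participants, power for a 66% change stays high throughout this range.

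**The case against.** The best defence is that Section 9.1 is a lone outlier. Every other place that names a sample for the primary FECa says fasting, so the sentence may be leftover text (an inference), and a careful analyst would follow the endpoint. As scheduled, the Section 9.1 version cannot be formed at baseline, which limits the scope for choosing between two finished results. The study also describes itself as primarily exploratory.

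Much of this stands. It shows which version is probably intended and lowers the risk of selection. It does not remove the conflict, because Section 9 itself does not fix the definition for completers. A missing sample at one end of each version also invites ad hoc substitution.

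A reader might go further and infer that the choice of formula could reverse the sign of the effect. The Background (Section 2.2) reports that FECa in earlier trials was below placebo over 0-6 and 6-12 hours but raised over 12-24 hours, with 24-hour urinary calcium slightly increased. The documents do not support that inference here. Those data come from once-daily doses of 5 to 30 mg, with no second dose covering the later window, whereas this trial doses every 12 hours. The 24-hour figure there is total excretion, not FECa. Section 2.2 also reports that twice-daily dosing lowered urinary calcium excretion in ADH1. The earlier data show that timing matters; they do not predict a reversal.

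**Conclusion.** The point holds as a conflict in the definition of the primary variable. Section 9.1 is wrong as written: it disagrees with Sections 1.1 and 3 on urine, blood and time window, has no matching baseline blood draw, and has no sample-size basis. The repair is not confined to 9.1, because the fasting and spot-urine definition has no scheduled Day 6 urine.

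The likely effect on the trial's conclusion is limited if the true reduction is near the 66% seen in ADH1. With 15 participants, power for that change is at least 0.977 up to an assumed SD of 60%. This rests on the assumed SDs and on the ADH1 effect carrying over to PSH. The text should still be corrected before analysis, since it concerns the only primary test and costs little.

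**What to change.** 1. Replace the FECa text in Section 9.1 with the definition from Sections 1.1 and 3: fasting Day -1 to the fasting morning of Day 6, or the last fasting measurement on encaleret 162 mg BID. Print the formula.
2. Repeat that definition in Section 9.4.2 for all participants, not only those who stop early or reduce the dose.
3. Reconcile Table B with it. Either add a fasting spot urine (Ca, Cr) on the on-treatment mornings through Day 6, or name the scheduled 16-24 hour timed collection as the on-treatment urine and say that it differs in type from the baseline spot sample.
4. Label any 24-hour FECa as exploratory. The current exploratory list names fractional excretion and 24-hour total excretion, but not expressly a 24-hour FECa.

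Section 2.3.1 mentions the first 6 participants with PSH already exposed to encaleret. If they belong to this trial, a newly added sample cannot be obtained for their completed stay, so the text should state which urine is used for them.

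Cost: text changes in 9.1 and 9.4.2 and one Table B entry, with extra spot samples only if the first option in step 3 is taken. The stated power figures do not change, because they already rest on fasting FECa.

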9.2 Sample Size Determination

The proposed clinical trial is primarily exploratory and preliminary data is limited. The primary study endpoint is the percent decrease in FECa using the entire Treatment Population (all participants who received at least one dose of study drug). Participants withdrawing for any reason any time after receiving their first dose of the study drug will remain in the Treatment Population, and the final FECa used will be the last fasting timepoint during which the patient was taking encaleret 162 mg BID.

Power calculations were based on the prior experience with encaleret in ADH1. In the ADH1 cohort, during a 5-day dosage escalation study (period 1), when 6 subjects were on the maximal dose of 162 mg BID for 3 days, the Mean (Standard deviation) of the Day 6 change in fasting FECa from baseline was -66 (20) % (unpublished data). Using a two-tailed 0.05 level paired t-test, we found that 15 participants yielded 80% power to detect a percent change of 16%; 10 participants yielded 80% power to detect a percent change of 20% and 5 participants yielded 80% to detect a percent change of 34%. Given the mean reduction in FECa was 66% in the ADH1 cohort (and the kidneys of participants with PSH might be expected to respond even more robustly to encaleret), we anticipate even a sample size of 5 would be sufficient to confirm the proof-of-principle effect on FECa.

Nevertheless, we plan to enroll up to 15 participants in this study in order to increase the likelihood that we include participants with a range of residual parathyroid tissue and to include participants with recent hypoparathyroidism. This will allow for sub-group analysis (see Section 9.3), which will be exploratory and hypothesis generating.

Of note, we plan to enroll only 5 participants with recent PSH (Cohort 2), because we anticipate some challenges in enrolling this population. More than 5 participants may be impractical to enroll in a reasonable amount of time.

9.3 Populations for Analyses

- **Treatment Population:** All participants who received at least one dose of study drug
- **Permanent hypoparathyroidism (Cohort 1):** Participants with long-standing hypoparathyroidism who received at least one dose of study drug
- **Recent Hypoparathyroid population (Cohort 2):** Participants with recent hypoparathyroidism who received at least one dose of study drug
- **“PTH-Clamp” Population:** Participants whose iPTH did not increase more than 10 pg/mL on encaleret

- **“Aparathyroid” Population:** Participants whose absolute iPTH level was less than 10 pg/dL throughout the study
- **Hyperthyroid Population:** Participants whose TSH is less than the lower limit of normal for the assay during the treatment phase of the study
- **Normothyroid Population:** Participants whose TSH is in the normal range during the treatment phase of the study
- **Thyroid Cancer Population:** Participants with a history of thyroid cancer

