- Percent change in Fractional Excretion of Calcium (FECa) from baseline (Screening visit) to the final day of treatment (Day 6 or the last measurement while on encaleret). FECa calculated using fasting blood levels and spot urine collection.
- Change in blood iPTH comparing average baseline iPTH to average peak iPTH on encaleret. The average baseline iPTH will include all baseline iPTH levels from the screening visit, Day -1, and pre-dose on Day 1. The average peak iPTH will average the peak iPTH levels on every day the patient is on encaleret (days 1 to 5). An increase in iPTH will be considered clinically significant if there is an increase both by 50% AND by more than 10 pg/dL.
- Change in 1,25-(OH)₂ Vitamin D on encaleret comparing the maximal level prior to receiving calcitriol (On Days 3-5) to baseline (Average of Day 1 Pre-dose levels). Increase will be considered significant if there is an increase of more than 50%. Participants who receive calcitriol prior to Day 3 will be excluded.
- Pharmacodynamic endpoints measured over 5 days of encaleret therapy:

- Blood iPTH – Absolute levels and change from baseline
- Albumin-corrected blood calcium – Absolute levels and change from baseline
- Ionized Calcium – Absolute levels and change from baseline
- Urinary calcium clearance (fractional excretion and 24-hour total excretion) – Absolute levels and change from baseline
- Serum levels of 1,25-(OH)₂ Vitamin D – Absolute levels and change from baseline
- Blood intact FGF23 (iFGF23) and C-terminal FGF23 (cFGF23) – Absolute levels and change from baseline
- Urine cAMP and citrate – Absolute levels and change from baseline
- Blood bone resorption marker, collagen cross-linked C-telopeptide (CTX) – Absolute levels and change from baseline
- Blood bone formation marker, blood procollagen type 1 N-propeptide (P1NP) – Absolute levels and change from baseline
- PK parameters such as maximum plasma concentration (C_{max}), time to maximum plasma concentration (t_{max}), apparent terminal half-life (t_{1/2}).
- Change in components of urine including: supersaturation, sodium, potassium, calcium, magnesium, chloride, phosphorus, sulfate, citrate excretion, oxalate, pH, uric acid, creatinine, osmolality, ammonium, urea nitrogen, protein catabolic rate

Study Population: Enrollment up to 30 male or female participants to achieve 15 to enter the treatment phase. Two cohorts:
Cohort 1: Permanent PSH (>1 year after surgery) with minimum of 7 and up to 10 participants

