Recent and ongoing phase 2 studies of encaleret in Autosomal Dominant Hypocalcemia type 1 (ADH1) due to gain-of-function variants in the CaSR, confirm the ability of encaleret to decrease urinary calcium and raise blood calcium. However, the net effect of encaleret on urinary and blood calcium in this situation is a result of the combined effect of both renal CaSR inactivation and increased PTH signaling. Patients with ADH1 have intact and functional parathyroid glands, so there is a rapid and robust increase in PTH secretion with encaleret therapy. To understand the PTH-independent effects of encaleret on calcium homeostasis, we will study patients with PSH treated with encaleret. The results of this study may also inform the potential role of encaleret in treating patients with PSH.

While it is predicted that calcilytics will act primarily at the kidneys in PSH to increase calcium reabsorption, this study also has the potential to inform the PTH-independent effects of encaleret on other aspects of bone and mineral homeostasis, such as active vitamin D (1,25 dihydroxyvitamin D) generation from action on 1- α hydroxylase, and/or bone turnover.

There is also the theoretical possibility that encaleret may have the ability to increase PTH secretion in patients with PSH with residual but clinically insufficient parathyroid function. If this occurs, it may even be the case that encaleret treatment could restore a normal level of parathyroid function over time.

In this exploratory proof-of-principle study, patients with PSH will be treated with encaleret in order to further our understanding of the PTH-independent effects of CaSR modulation. In addition, this study may provide clinically relevant information about how encaleret could be used as either an independent or adjuvant therapy for patients with PSH.

Our primary analyses will include all participants who received at least one dose of the study drug. However, because patients with PSH have variable residual parathyroid tissue, we will also perform sub-group analyses on a “PTH-Clamp” population defined as those whose iPTH do not increase more than 10 pg/mL on encaleret and a “Aparathyroid” population defined as those whose absolute iPTH level are less than 10 pg/dl throughout the study. The biochemical response of these subpopulations may more accurately reflect the PTH-independent effects of CaSR modulation.

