4.2 Scientific Rationale for Study Design

The current clinical trial is a small proof-of-principle trial designed to explore PTH-independent effects of encaleret on calcium homeostasis and to determine the ability of a calcilytic to decrease urinary calcium excretion and raise blood calcium in patients with PSH. Encaleret has the potential to fill the unmet need of an oral medication for PSH that can maintain eucalcemia without increasing the risk of hypercalciuria and renal calcifications.

Our primary analyses will include all participants who received at least one dose of the study drug. However, sub-group analysis will also be performed on patients with recent PSH (cohort 2) to explore whether maximal PTH stimulation by a calcilytic can transiently increase PTH secretion in healing parathyroid glands. Patients with recent PSH have the potential to either

have resolution of their hypoparathyroidism or progression to permanent hypoparathyroidism. They will likely respond to encaleret at the kidney level very similarly to cohort 1 in terms of the primary endpoint, FECa, because their kidneys presumably function the same. However, since these patients may have reversible parathyroid gland damage, they may be more likely to increase PTH secretion in response to maximal stimulation by encaleret. It should be noted that the dose of encaleret that is being used will be biologically sensed as profound hypocalcemia to a degree that would never be experienced by a patient with PSH and as such may function as a much more potent stimulator of PTH secretion.

Furthermore, because patients with PSH have variable residual parathyroid tissue, we will also perform exploratory sub-group analyses on a “PTH-Clamp” population whose iPTH did not increase more than 10 pg/mL on encaleret and a “Aparathyroid” population whose absolute iPTH level was less than 10 pg/dl throughout the study. The biochemical response of these subpopulations will likely more accurately reflect PTH-independent effects of CaSR modulation.

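### Two iPTH cut-offs are written in pg/dL, 100 times below the pg/mL limit beside them, so the Aparathyroid population and the iPTH-rise rule do not work as written

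*Combined protocol and SAP*

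**What the plan says.** Three iPTH rules use the number 10.

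- PTH-Clamp population, Section 9.3: "Participants whose iPTH did not increase more than 10 pg/mL on encaleret". Sections 2.1 and 4.2 use the same unit.
- Aparathyroid population, Section 9.3: "Participants whose absolute iPTH level was less than 10 pg/dL throughout the study". Section 2.1 has "population defined as those whose absolute iPTH level are less than 10 pg/dl throughout the study" and Section 4.2 has "population whose absolute iPTH level was less than 10 pg/dl throughout the study". In both, the pg/mL limit for PTH-Clamp stands in the same sentence.
- Clinically significant rise, Section 1.1, repeated in the Section 3 table: "An increase in iPTH will be considered clinically significant if there is an increase both by 50% AND by more than 10 pg/dL".

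The rise is measured from the average of all baseline iPTH values (screening, Day -1, Day 1 pre-dose) to the average of the daily peaks on Days 1 to 5. The 1,25-(OH)2 vitamin D endpoint compares the highest pre-calcitriol value on Days 3 to 5 with the average of the Day 1 pre-dose values, and calls a rise above 50% significant.

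Section 9.4.7 analyses the primary and secondary endpoints in every Section 9.3 population. Section 9.2 describes the subgroup work as exploratory. No assay detection limit, iPTH reference range or rule for undetectable results is given.

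**The concern.** The same number appears with units that differ 100-fold, in rules that are meant to work together. The pg/dL unit recurs in five places (Sections 1.1, 2.1, 3, 4.2 and 9.3), and neither affected rule is ever stated in pg/mL. A programmer working from the text has no correct version to fall back on.

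The primary objective is the PTH-independent effect, but the primary analysis takes everyone dosed, whatever their PTH does. Section 4.2 expects the two PTH-defined populations to reflect that effect more accurately, in hedged terms, and Section 2.1 says only that they may. If one of them cannot be formed as written, part of the supporting evidence is lost or is settled after the data are seen. Section 2.3.1 reports PTH in the low or low-normal range on drug in the first six participants, so residual secretion is a live question.

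**Working it through.** **Inputs.** The cut-offs are those listed above. Draw counts come from Table C. The baseline has 4 iPTH values: screening, Day -1, and two Day 1 pre-dose. On-drug iPTH draws number 6 on Day 1, 5 on each of Days 2 to 4, and 7 on Day 5. The counts for Days 2 to 5 include that morning's pre-dose draw, and Day 5 leaves out the 24-hour draw. For 1,25-(OH)2 vitamin D there are 2 baseline values and one morning value on each of Days 3, 4 and 5. The plan derives no figure here that could be reproduced, so the check starts from the unit.

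**1. Conversion.** 1 dL = 100 mL, so 10 pg/dL = 10/100 = 0.1 pg/mL. Ratio to the PTH-Clamp limit: 10/0.1 = 100.

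**2. Rise rule.** For baseline B and absolute cut-off C, the rise needed is max(0.5 × B, C). The absolute part matters only when B < 2C. As written, that is B < 0.2 pg/mL; with C = 10 pg/mL, it is B < 20 pg/mL.

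| Baseline (pg/mL) | Rise needed as written | Rise needed if 10 pg/mL |
|---|---|---|
| 2 | 1 | 10 |
| 5 | 2.5 | 10 |
| 10 | 5 | 10 |
| 20 | 10 | 10 |
| 30 | 15 | 15 |

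**3. Clash with PTH-Clamp.** Take 4 to 7 pg/mL. The rise is 3 pg/mL, or 3/4 = 75%. That exceeds 50% and 0.1 pg/mL, so it is significant; it does not exceed 10 pg/mL, so it is also within PTH-Clamp. With 10 pg/mL in both rules, and the same rise used for both, no one can meet both.

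**4. Aparathyroid.** The literal rule needs iPTH below 0.1 pg/mL at every draw. If the assay limit L is above 0.1 pg/mL (an assumption), no measurable value qualifies. Undetectable values qualify if set to zero. They do not qualify if set to L, or to L/2 when L/2 is 0.1 or more. The population therefore runs from nobody to the always-undetectable participants.

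**5. Peak against mean.** Simulated with no drug effect, log-normal draws and assumed CVs of 10%, 20% and 30%:

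- iPTH, independent draws: apparent rise of +13%, +27% and +43%. Participants passing the 50% part: 0%, 7% and 36%.
- iPTH, 80% of log-variance shared within a day: +6% to +20% across the same CVs. Passing: 0%, 2% and 13%.
- 1,25-(OH)2 vitamin D, maximum of 3 independent values against a mean of 2: +9% to +31%. With only one usable value the rise is roughly CV²/2, at most 0.30²/2 = 4.5%.

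With the absolute part at 10 pg/mL and CV 30% (independent draws), false iPTH responders are about 0% at a baseline of 5 pg/mL and 0.2% at 10. They become material higher up: roughly 10% at 15 and 30% at 20.

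**The case against.** The best defence is that nobody would apply the literal unit. Sections 2.1 and 4.2 put pg/mL and pg/dl in one sentence, and an analyst would see the slip. That is plausible, but it leaves the choice to whoever notices, possibly with the data in hand.

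A reader might infer that the Aparathyroid population is certainly empty. The documents do not support that: they expect some undetectable PTH and give neither an assay limit nor a rule for such values.

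A reader might also infer that the main PTH-independent conclusion is compromised. It is not. PTH-Clamp is in pg/mL throughout, the primary FECa analysis uses the Treatment Population, and the sample size does not involve iPTH.

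On peak against mean, it is tempting to claim that the trial would almost always declare a PTH rise. The plan names no test for these endpoints. Section 9.4.1 gives descriptive summaries, Section 9.4.9 says mixed models may be used, and significance is judged by thresholds. Peaks also have a rationale: Section 2.2 describes iPTH elevation over 3 to 4 hours after dosing, which a pre-dose-only comparison could miss. For vitamin D, calcitriol may start on Day 3, leaving some participants fewer than three values. Home calcitriol stops after Day -2, so a flat no-effect course is doubtful. These points stand. They limit the size of the bias but do not remove the upward lean of a maximum set against a mean.

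**Conclusion.** The unit error is certain from the text, and the 100-fold factor needs no assumption. That the absolute part of the rise rule is idle at baselines of 0.2 pg/mL or more follows by arithmetic. That Aparathyroid shrinks to at most the always-undetectable participants assumes an assay limit above 0.1 pg/mL. The damage is confined to an exploratory iPTH endpoint and one hypothesis-generating subgroup. It should be corrected, but it does not threaten the primary result.

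The peak-against-mean lean is a separate, secondary point. Its direction follows from the definitions; its size rests on assumed CVs and correlations: about +6% to +43% for iPTH, and up to about +9% to +31% for 1,25-(OH)2 vitamin D with three independent values, less with fewer. Correcting the unit removes nearly all false iPTH responders at baselines of 10 pg/mL or less, but not at higher ones.

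**What to change.** 1. Use one unit for every iPTH cut-off in Sections 1.1, 2.1, 3, 4.2 and 9.3. From the PTH-Clamp definition, pg/mL appears intended; the sponsor should confirm this before the populations are derived.
2. In Section 9.3, state the assay limit and how values below it count, both for Aparathyroid membership and for percent change. State also which on-drug iPTH value defines the PTH-Clamp increase, so that it and the rise rule use the same quantity.
3. Keep the peak iPTH summary, and report beside it the time-averaged on-drug mean over all scheduled draws, post-dose draws included, against mean baseline. For 1,25-(OH)2 vitamin D, add the mean of the pre-calcitriol values on Days 3 to 5 against mean baseline.

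The cost is text edits and some extra derived variables from samples already scheduled. No new data, visits or participants are needed.
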